#### METHODOLOGY

At the inclusion visit, the patient will be given the information sheet (Annex 1) and, if they agree, they will be asked to sign the informed consent. Once included in the study, they will be randomly assigned to one of the two study groups in order of consecutive inclusion.

The project will be presented to the Ethics Committee of the Autonomous University of Barcelona UAB.

SAMPLE SIZE CALCULATION

The aim of this study was to assess the difference between a decrease in the diameter of the abdominal circumference in a group of women, before and after radiofrequency treatment. The aim is to be able to declare a difference of 2 points or more as significant, taking the SD from published research that gives around 8.0 with a confidence level of 95%, a power of 80% and a correlation coefficient of 0.70 between the values of abdominal circumference before and after treatment. These are taken from the article published by Duarte et al. in 2015 (Duarte et al, 2015), and the following results are obtained according to EPIDATA: 15 pairs of data will then be taken: Before and after the application of RF.

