## OBJECTIVES

MAIN OBJECTIVE.

- To understand the effect of high-power resistive capacitive radiofrequency on the decrease of body fat and changes in biochemical markers linked to inflammation.
  SIDE OBJECTIVES.
  - 2. To assess the role of radiofrequency in reducing abdominal fat.
  - 3. To assess and compare the decrease in abdominal circumference measured by anthropometric tape measure, Body Mass Index, Waist-to-Hip Ratio and skinfold before and after RF treatment.
  - Evaluate changes in Human IL-6, Human TNF-alpha, Human-Leptin, Human-Adiponectin, Human-Resistin, C-reactive protein values before and after RF sessions. Evaluar y comparar el impacto de la calidad de vida antes y después del tratamiento con radiofrecuencia.
  - 5. To assess and compare the impact of quality of life before and after radiofrequency treatment.

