## [1] Sample size. Comparison for paired means.

Data:

Mean differences to be detected:	6.442
Standard Deviation of the differences:	8.221
Level of confidence:	95.0%
sults.	

Results:

Stat. Power (%)	Number of Pairs
80.0	15

Inclusion criteria:

- Men and women from 20 to 60 years old

- With Waist-Hip Index. Greater than: 0.84 normal for women. 94 normal for men.

- Body Mass Index that is defined as: Overweight: Between 25-29.9. Obesity: 30 or higher.

- Measurement of Visceral Fat per Inbody greater than 9, which is what is considered Normal.

- Signed informed consent (Annex 1).

Exclusion Criteria:

- Contraindication to the use of radiofrequency: pregnancy, metal prostheses, active infection.

- Patients with a history of cancer, chemotherapy and radiotherapy treatments.

- Not having diabetes or metabolic disease.

MEASUREMENTS

Body Mass Index, Waist-t-Hip ratio and visceral fat:

Body Mass Index is calculated as follows: Body Weight (Kg) ÷ (Height in cm)2

Waist-to-Hip Ratio: According to World Health Organization guidelines, the waist should be measured at the midpoint between the last palpable rib and the top of the iliac crest (upper edge of the pelvis). The hip should be measured at the point of maximum circumference, i.e. the point where the buttocks reach maximum width. Both measures should be taken immediately after the air in the lungs is exhaled. It is important to keep your feet together and your arms in a normal position next to your body. It is advisable to take each measure twice and repeat it if different results are obtained (WHO 2008). The caliper takes the thickness of the abdominal wall at 5 cm in an oblique line towards the navel on the right and left side.

The visceral fat value: will be measured using, in addition to the MRI method, an Inbody electrical impedance equipment, in the first and last session.

TREATMENT

Each patient will have 4 active, automatic plates placed on the abdomen, two on the right side of the midline and two on the left side. Energy will be applied for 50 minutes, controlling the temperature. Subsequently, 15 minutes of Capacitive and Resistive manual electrodes will be applied to the abdomen, simultaneously, 20 minutes of Lymphatic Drainage placing one active plate in the foot and the other in the lumbo-dorsal area. You will be informed that you will only feel comfortable warmth. Five sessions will be applied from Monday to Friday resting Saturday and Sunday, for 2 weeks. Total 10 sessions.

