#### Statistical analysis and expected results

The statistical analysis of the results will be performed using the Software Package for Social Sciences (SPSS 24.0.).

A Kolmogorov-Smirnov test will be applied, if the data behaves normally, parametric tests will be applied. If not, non-parametric tests will be performed.

The differences between proportions will be analyzed using Fischer's exact test. The differences between the medians will be assessed using the Student's t-test for paired samples and independent samples. To determine the correlation between two quantitative variables, Pearson's correlation coefficient will be used.

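### The plan randomises to two groups but describes and sizes only one; if there is one, a before/after change cannot be attributed to radiofrequency

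*Combined protocol and SAP*

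**What the plan says.** METHODOLOGY states that, after inclusion, patients "they will be randomly assigned to one of the two study groups in order of consecutive inclusion". The groups are not named, and no allocation ratio, random list or concealment method is given.

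The rest of the available text reads as one treated group:

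- SAMPLE SIZE CALCULATION concerns a change in abdominal circumference "in a group of women, before and after radiofrequency treatment" and concludes that "15 pairs of data will then be taken: Before and after the application of RF". The software printout that follows is headed as a comparison of paired means.
- TREATMENT opens with "Each patient will have 4 active, automatic plates placed on the abdomen" and describes no sham, untreated, delayed or alternative regimen.
- In OBJECTIVES, every comparison that is spelled out is before versus after treatment.
- STUDY PROTOCOL plans one treatment for 20 candidates, with no split.

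Two statements point the other way. Statistical analysis and expected results lists a t-test "for paired samples and independent samples", and Fisher's exact test for proportions, without saying which groups or endpoints they compare. And OBJECTIVES is worded causally: the main objective is "To understand the effect of high-power resistive capacitive radiofrequency on the decrease of body fat", together with changes in inflammatory markers, and side objective 2 is "To assess the role of radiofrequency in reducing abdominal fat".

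**The concern.** The number of groups decides what the trial can conclude, and the plan gives two incompatible answers.

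If there is one group, a before/after change mixes any radiofrequency effect with everything else that moves waist or fat over the same weeks. The candidate criteria under STUDY PROTOCOL include a commitment to diet and exercise throughout treatment. Entry selects on high waist-hip ratio, BMI and visceral fat. The STUDY PROTOCOL criteria also set cut-offs of 80 cm (women) and 94 cm (men) on a measure abbreviated CC, read here as waist circumference, which is the sized endpoint. Regression to the mean is therefore possible. This is a problem of attribution, not of an inflated type I error: the paired test would correctly detect a change but could not say what caused it. Reporting such a study as randomised would also be wrong.

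If there are two groups, the randomised comparison has no defined arms, no named endpoint and no power calculation.

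**Working it through.** All powers use the noncentral t distribution, two-sided 5%. The plan does not state sidedness, but two-sided reproduces its figure.

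**1. The plan's own figure.** Printout inputs: difference 6.442, SD of differences 8.221, 95% confidence, 80% power. For n pairs the noncentrality is λ = δ√n/σ, with n − 1 degrees of freedom.

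- n = 15: λ = 6.442 × √15 / 8.221 = 3.03; power 80.6%.
- n = 14: power 77.3%.

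So 15 is the smallest number reaching 80%. The printout is a within-patient calculation and contains no between-group comparison.

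**2. Second input set.** The prose gives SD 8.0, correlation 0.70 and a difference of 2 points. SD of differences = 8.0 × √(2 × (1 − 0.70)) = 6.197. That the prose and printout inputs disagree is a separate matter; both are carried so that the result does not depend on choosing one.

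**3. If there is one group (illustration).** Give radiofrequency no effect and assume a background fall in waist of 1 or 2 cm. These falls are assumptions, kept below the 2.9 to 3.95 cm treated reduction cited in RADIOFREQUENCY AND LIPOLYSIS. Chance that the paired test is significant:

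| Pairs | SD of differences | 1 cm fall | 2 cm fall |
|---|---|---|---|
| 15 | 6.197 | 9% | 21% |
| 15 | 8.221 | 7% | 14% |
| 20 | 6.197 | 11% | 28% |
| 20 | 8.221 | 8% | 18% |

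Each is a correct detection of a change whose cause is not radiofrequency. The documents do not allow the size of regression to the mean to be derived, so none is claimed.

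**4. If there are two groups.** Reuse each of the plan's before/after input sets, unmixed, as a between-group difference in change and SD of change (an assumption). λ = δ / (σ√(1/n₁ + 1/n₂)), with n₁ + n₂ − 2 degrees of freedom. For 6.442 and 8.221 at 10 v 10, λ = 0.7836/√0.2 = 1.75.

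| Groups | 6.442, SD 8.221 | 2, SD 6.197 |
|---|---|---|
| 7 v 8 (15 in all) | 29% | 9% |
| 10 v 10 (20 in all) | 38% | 11% |
| 15 v 15 | 54% | 14% |

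For scale, 80% power with equal groups and no dropout would need about 27 per group on the printout inputs, or 152 per group on the prose inputs.

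**The case against.** The strongest reply is that the randomisation sentence is a stray line. The methodology summary in BRIEF DESCRIPTION OF THE PROJECT goes from consent straight to the 15 pairs without mentioning randomisation. A single-arm before/after study is a legitimate design, and side objectives 3 to 5 are answerable without a control. This has force and supports the one-group reading without proving it. Even so, the sentence must go, and the main objective and side objective 2 still claim more than that design can deliver.

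Some pages were not available for review, and a group definition could sit there. That is why the consequence is stated conditionally. Even if the arms are defined there, the sizing remains paired and the analysis section ties its independent-samples test to no endpoint.

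Two points on evidence stand. The word for the plates is an electrode term, not a contrast with sham; only the statement that each patient receives them carries weight. And the diet commitment appears only in the STUDY PROTOCOL text, which differs from METHODOLOGY on number (20 against 15 pairs), entry criteria and schedule: METHODOLOGY says "Five sessions will be applied from Monday to Friday resting Saturday and Sunday, for 2 weeks", STUDY PROTOCOL ten sessions over five weeks. It is unclear which text governs. Attribution fails without the diet commitment, though, because no concurrent comparator is described.

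Finally, the background falls are assumed, and attribution fails whatever the significance rate. Those percentages illustrate the problem; the conclusion does not rest on them.

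**Conclusion.** The concern holds, and the plan must be corrected before it is followed. The contradiction over the number of groups is in the text and rests on no assumption.

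With one group, the main objective and side objective 2 cannot be answered as worded. With two, the stated 80% power does not apply to the randomised comparison: illustrated power is 29% to 54% on the printout inputs and 9% to 14% on the prose inputs. Those figures assume that before/after inputs can stand in for between-group ones and that the groups are equal or nearly so; the documents give neither between-group inputs nor an allocation ratio.

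**What to change.** State whether there are one or two groups, and reconcile OBJECTIVES, METHODOLOGY, the treatment and analysis sections and the STUDY PROTOCOL text accordingly. Say whether the diet and exercise commitment and the waist cut-offs apply to the study described in METHODOLOGY. The differing schedules must also be reconciled; no view is taken on which is right.

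**If one group:**

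1. Delete the randomisation sentence.
2. Say what the independent-samples t-test and Fisher's exact test compare, or remove them.
3. Reword the main objective and side objective 2 as before/after change. The objective list in STUDY PROTOCOL already speaks of a decrease without attributing it to treatment.
4. Add a limitation such as: *One group is compared before and after; the change may reflect radiofrequency, diet and exercise, regression to the mean and time, and cannot be attributed to radiofrequency alone.* Keep the diet and exercise words only if that commitment is confirmed.

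Cost: text edits only. The downside is a weaker but correct claim.

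**If two groups already exist:**

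1. State what each receives and whether the diet and exercise commitment applies to both. If both are active, say that the comparison is between the two treatments.
2. Describe how the random list is made and concealed.
3. Name the between-group difference in change as the primary comparison. The independent-samples t-test on change would serve, and a baseline-adjusted analysis is an efficient option. Name its counterpart under the plan's switch to non-parametric tests.
4. Restate the power for that comparison.

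Cost: text edits and one power calculation. The downside is a lower stated power.

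Adding a control group or more patients is not part of this fix.

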# **BRIEF DESCRIPTION OF THE PROJECT**

The burden of obesity has increased globally in recent decades and its association with insulin resistance and related cardio-metabolic problems. Radio frequency (RF) is a form of high-frequency electromagnetic energy that works by heating tissues. Its action aims to increase cellular metabolism. Its action aims to increase cellular metabolism. Frequencies around 1 MHz are used, which are more effective in the cell, but with high power, adjustable temperature and treatment area greater than 200 cm2, which mechanically destroys the adipose cells, without damaging the skin, blood, vessels, nerves or connective tissues.

The lymphatic system eliminates lidis, reducing tissue volume. Magnetic resonance imaging (MRI) has similar accuracy to CT scans, but with no exposure to ionizing radiation. The MRI method for quantifying abdominal adiposity is effective. Chronic inflammation that lasts a long time is characterized by the presence of lymphocytes, macrophages, proliferation of blood vessels and connective tissue, it is considered a feature of metabolic syndrome, characterized by secretion of inflammatory adipokines usually from adipose tissue, leptin, interleukin (IL-6), tumor necrosis factor  $\alpha$  (TNF- $\alpha$ ), monocyte chemoattractant protein 1 (MCP-1) and resistin. RNA markers involved in apoptotic processes revealed that tissue exposed to RF treatment demonstrated a pro-apoptotic reaction. Therefore, we propose to apply through four channels and four electrodes of 200 cm2 a powerful RF energy raising the temperature and thus reducing visceral fat, evaluating the biochemical parameters of inflammation of the adipocyte.

MAIN OBJECTIVE: To understand the effect of high-power resistive capacitive RF on the decrease of body fat and changes in biochemical markers linked to inflammation.

METHODOLOGY: at the inclusion visit, the patient will be given the information sheet (Annex 1) and, if they agree, they will be asked to sign the informed consent. We aim to declare a difference of 2 points or more as significant, taking the SD from published research that gives around 8.0 with a confidence level of 95%, a power of 80% and a correlation coefficient of 0.70 between the values of abdominal circumference before and after treatment. Noted by Duarte et al. in 2015. We have obtained by EPIDATA that 15 pairs are needed.

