# **STUDY PROTOCOL**

The study will be carried out to 20 candidates who want to participate free of charge in exchange for their testimony and their commitment to the study.

The treatment will be carried out with the only technology on the market from Capernergy Medical, with its C-400 equipment, approved and authorized by the Ministry of Health, with its own national and international patents.

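### The 15 pairs come from a difference of 6.442, not the stated 2 points; at 2 points, 15 pairs give 14% to 21% power instead of 80%

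*Combined protocol and SAP*

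**What the plan says.** **Narrative.** The sample-size paragraph under METHODOLOGY sets the target: "The aim is to be able to declare a difference of 2 points or more as significant, taking the SD from published research". The SD is put at around 8.0, with 95% confidence, "a power of 80% and a correlation coefficient of 0.70 between the values of abdominal circumference before and after treatment". BRIEF DESCRIPTION OF THE PROJECT repeats these inputs and concludes: "We have obtained by EPIDATA that 15 pairs are needed".

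**Printout.** The section headed [1] Sample size. Comparison for paired means. lists "Mean differences to be detected" as 6.442 and "Standard Deviation of the differences" as 8.221. At 95% confidence and 80% power it returns 15 pairs. It carries no unit and no outcome label.

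**Design around it.** The calculation is for one group measured before and after treatment. METHODOLOGY also says patients will be "randomly assigned to one of the two study groups in order of consecutive inclusion", and Statistical analysis and expected results plans "Student's t-test for paired samples and independent samples". STUDY PROTOCOL gives another number: "The study will be carried out to 20 candidates who want to participate". OBJECTIVES lists abdominal circumference among the side objectives.

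**The concern.** The narrative and the printout share the answer of 15 but not the inputs. The difference to detect is about three times larger in the printout (6.442 / 2 = 3.2), and nothing in the documents explains 6.442 or connects it to 2 points. The SDs do not match either: 8.0 with a correlation of 0.70 does not lead to 8.221.

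This is the only sample-size justification in the documents. A reader will take from it that a 2-point change would be found four times out of five. If that is untrue, a null result says little about a 2-point effect, yet the stated power invites the opposite conclusion.

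**Working it through.** **Method.** Two-sided 5% paired t-test. With n pairs, true change δ and SD of differences s, power is the probability that a noncentral t with n − 1 degrees of freedom and noncentrality λ = (δ/s)√n falls beyond ±t(0.975, n − 1). The plan does not state sidedness; the first step supports two-sided.

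**1. Reproduce the printout.** δ = 6.442, s = 8.221, n = 15:

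- λ = (6.442/8.221) × √15 = 0.7836 × 3.873 = 3.03, critical value 2.145, power 80.6%.
- With n = 14 the power is 77.3%.

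So 15 is the smallest n reaching 80%. A one-sided t-test would give 12, a two-sided normal approximation 13 and a one-sided one 11. Only the two-sided t-test gives 15.

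**2. SD of differences under the narrative.** The text does not say what 8.0 is the SD of.

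- SD of the measurement, equal before and after: s = 8.0 × √(2 × (1 − 0.70)) = 8.0 × √0.6 = 6.20.
- SD of the differences: s = 8.0. The stated correlation then plays no part.
- The printout's own value: s = 8.221. With r = 0.70 this would need a measurement SD of 8.221/√0.6 = 10.6. With a measurement SD of 8.0 it would need r = 1 − 8.221²/(2 × 64) = 0.47.

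**3. Results at a 2-point change.**

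| | s = 6.20 | s = 8.0 | s = 8.221 |
|---|---|---|---|
| λ with 15 pairs | 1.25 | 0.97 | 0.94 |
| Power, 15 pairs | 21.4% | 14.7% | 14.2% |
| Power, 20 pairs | 27.8% | 18.6% | 17.9% |
| Pairs for 80% power | 78 | 128 | 135 |
| Pairs, normal approximation | 75.3 | 125.6 | 132.6 |
| Change detectable with 80% power, 15 pairs | 4.8 | 6.2 | 6.4 |
| Change detectable with 80% power, 20 pairs | 4.1 | 5.3 | 5.4 |
| Smallest significant observed change, 15 pairs | 3.4 | 4.4 | 4.6 |

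The normal approximation is (1.960 + 0.842)² × (s/2)², for example 7.849 × 9.6 = 75.3. The last row is 2.145 × s/√15. A simulation of 200,000 runs with 15 pairs gave power of 21.6% at s = 6.20 and 14.1% at s = 8.221.

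**4. What would make 15 pairs enough at 2 points?** An SD of differences of 2.57. With a measurement SD of 8.0 that needs r = 1 − 2.57²/128 = 0.948, against the stated 0.70.

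**5. Two groups.** No allocation is given. Assume, for illustration, that the 20 are split 10/10.

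- Ten pairs in one group have power 15% / 11% / 11% at 2 points, and 60% even for the printout's own 6.442 and 8.221.
- A between-group difference of 2 in change has power 11% / 8% / 8% (two-sample t-test on change scores).

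**The case against.** **The 2 points may mean the observed difference that reaches significance.** The wording allows this, but it fails too. With 15 pairs an observed change of 2 is significant only if the observed SD of differences is below 2 × √15/2.145 = 3.6, well under every planning SD.

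**The test may be one-sided.** That lowers the requirement to 61 / 101 / 106 pairs and raises power with 15 pairs to only 32% / 23% / 23%. It also no longer reproduces the printed 15.

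**The correlation matters only if 8.0 is the SD of the measurement, so 78 pairs and 21% are the natural reading.** This is fair. The 135 and 14% join the narrative's target to the printout's SD, a pairing the plan never states, and are best read as the far end of a range. The conclusion is the same at either end.

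**The unit of points is not given and the cited source cannot be seen here.** True. An SD of differences near 2.6 would rescue the claim, but no figure in the documents supports one.

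**Removing the 2-point target may abandon the real design goal.** This stands as a caution. The documents do not show whether 2 or 6.442 was intended, so the sponsor has to say.

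**The printout's target may be optimistic.** RADIOFREQUENCY AND LIPOLYSIS reports average girth reductions of 2.9 to 3.95 cm. If the printout is in cm (an assumption), 6.442 lies above that range. Across the three SDs, 15 pairs then have power of about 25% to 39% at 2.9 and 41% to 63% at 3.95. Restating the printout is therefore honest only if the low power at smaller changes is stated beside it.

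**The two-group figures rest on an assumed split.** Correct, and the main point does not depend on them.

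**Conclusion.** The concern holds. The printout is internally correct, but it supports 80% power for a change of 6.442 with an SD of differences of 8.221. It does not support the 2-point claim made in two places. At 2 points, 15 pairs give 14% to 21% power and 20 pairs 18% to 28%; 78 to 135 pairs would be needed. The lower requirement rests on equal SDs before and after treatment, and all figures on a two-sided 5% paired t-test. The stated power is wrong and must be corrected. Even the corrected figure covers only a within-group change in a side objective. The documents show no calculation for the main objective or for any comparison between the two groups.

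**What to change.** Leave enrolment as it is, remove the 2-point claim from BRIEF DESCRIPTION OF THE PROJECT and METHODOLOGY, and use one set of inputs there and in the printout. Either of these is correct:

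- *Option A, the calculation that was run:* 15 pairs give 80% power (two-sided 5% paired t-test) for a mean before-after change of 6.44 with an SD of differences of 8.22; power at a change of 2 is about 14%.
- *Option B, measurement SD 8.0 and r = 0.70, with a matching new printout:* 15 pairs give 80% power for a change of 4.8 (20 pairs: 4.1); power at a change of 2 is about 21% (28%).

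Under either option add: *This power covers only the within-group before-after change in abdominal circumference, a side objective. No power calculation was made for the main objective or for comparisons between the two groups.*

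Before choosing, the sponsor should confirm the unit and source of 6.442 and 8.221, what 8.0 is the SD of, whether 15 is per group or in total, and how it relates to the 20 candidates in STUDY PROTOCOL.

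The cost is wording only, with no extra enrolment. The price is a less favourable stated detectable effect. If the sponsor instead wants to keep 2 points at 80% power, wording will not do: the numbers are the 78 to 135 pairs above.
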